3.2 Inclusion Criteria

Criteria for the diagnosis and therapy for Lyme disease can be found at “The clinical assessment, treatment, and prevention of Lyme disease, human granulocytic anaplasmosis, and babesiosis: clinical practice guidelines by the Infectious Diseases Society of America”⁵.

Patients with Lyme disease, post-therapy (N=100)

1. Age 18 or older.
2. Lyme disease diagnosed in the previous 13 months, fulfilling the case definition of confirmed or probable Lyme disease by the US Centers for Disease Control and Prevention (CDC) <https://www.cdc.gov/nndss/conditions/lyme-disease/case-definition/2017/>.
3. Completion of 1 course of antibiotics at least 3 months and up to 12 months between the end of the therapy and the xenodiagnostic procedure.
4. Antibiotic treatment fulfills the Infectious Diseases Society of America guidelines for the recommended therapy for Lyme disease⁵.

Patients with post-Lyme disease complaints at least 12 months from initial treatment (N=40)

1. Age 18 or older.
2. Diagnosed with confirmed or probable Lyme disease fulfilling the case definition of Lyme disease by the CDC <https://www.cdc.gov/nndss/conditions/lyme-disease/case-definition/2017/>.
3. Received recommended antibiotic therapy for Lyme disease⁵ at least 12 months between the end of the initial antibiotic therapy and the xenodiagnostic procedure.
4. Persistent or recurrent symptoms that began or worsened within 6 months of the diagnosis and treatment for Lyme disease.

Acute EM (N=40)

1. Age 18 or older.
2. EM diagnosed by the study physician.
3. Receiving antibiotic therapy for Lyme disease for less than 48 hours.

Lyme Arthritis (N=40)

1. Age 18 or older.
2. Lyme arthritis⁵⁰ and have not received antibiotic therapy for the disease.

Healthy volunteers (N=20)

1. Age 18 or older.
2. No prior history of Lyme disease.
3. Negative whole cell enzyme-linked immunosorbent assay (ELISA) or C6-based antibody test for Lyme disease.

Patients with recently diagnosed (acute) EM (within 48 hours of starting antibiotic therapy) and patients with untreated Lyme arthritis will be recruited in an attempt to increase the chances of finding a positive result by xenodiagnosis (an attempt of a “positive control”). While patients with acute untreated EM would be the best positive control group, it would be unethical to withhold therapy in these patients for the few days required for tick feeding, due to the risk of dissemination of the organism and possible morbidity. Patients with untreated Lyme arthritis will

be recruited to establish whether xenodiagnosis can be used to identify infection in late stage Lyme patients where the bacterium is known to be present. These patients have been infected for months and will not be harmed for delaying therapy for a few days. Lyme arthritis is a late manifestation of *B. burgdorferi* infection, and hematogenous dissemination already occurred at this late stage. Studies have shown that the presence or absence of previous antibiotic treatment is more predictive than the duration of untreated arthritis for the success of antibiotic therapy in Lyme arthritis.^{6,8,51-53} Similarly, patients who just started therapy for EM may still have live *Borrelia* in the skin and xenodiagnosis may be able to recover the bacteria (but culture of skin biopsies from patients with EM become negative very quickly - within one dose - on antibiotic therapy).

While treatment for Lyme disease will not be offered under this protocol, it may be available via different clinical research protocols or regular medical care at the study site. If not, treatment will be prescribed by the patient's primary care. For patients with untreated early Lyme disease (erythema migrans), antibiotics can be started at the same day of tick placement. For patients with untreated Lyme arthritis, antibiotics can be started after collection of xenodiagnostic ticks (usually 4-5 days, up to 7 days). For patients with Lyme arthritis, if less than 14 ticks fed successfully and if the participant agrees, antibiotic treatment can be delayed until after the repeat procedure (see Section 4.7).

Patients with acute EM and untreated Lyme arthritis will be able to re-enroll as Patients with Lyme disease, post-therapy. Therefore, in case of positive results, we will be able to compare between the procedures.

Negative control patients will include healthy volunteers from Lyme endemic areas who have never been diagnosed with Lyme disease and have a negative *B. burgdorferi* ELISA and C6 antibody titer.

3.3 Exclusion Criteria

1. No antibiotic therapy active against Lyme disease in the previous 3 months (except patients with acute EM). Prophylaxis with a single dose of doxycycline 200 mg is not an exclusion.
2. History of allergy to surgical tape or dressing.
3. History of severe reactions to tick bites (granuloma or systemic reactions).
4. Inability to maintain the dressing for any reason.
5. Pregnancy or lactation.
6. Unwillingness to use an effective method of birth control for the duration of participation in the study (women of child-bearing potential only) and for at least 3 months following the last tick placement.
7. Use of investigational therapy and devices during the time of the study and/or in the month prior to signing the informed consent.
8. Active severe skin disease, uncontrolled diabetes, cancer other than non-melanoma skin cancers, autoimmune disease requiring immunosuppressive therapy, or history of HIV, chronic viral hepatitis, or syphilis.
9. Oral or IV steroids in the previous 2 weeks (topical, nasal, inhaled, intra-articular, and replacement doses of steroids are not exclusions).

10. Any other condition that, in the opinion of the investigator, would make the patient unsuitable for enrollment or could interfere with the patient participating in and completing the study.
11. Refusal to participate in specimen collection and storage for future study related use.

3.4 Exclusion from Skin Biopsy Part of the Protocol

1. History of forming large thick scars (keloids) after skin injuries or surgery.
2. History of excessive bleeding after cuts or procedures.
3. Currently taking anticoagulants.
4. History of allergy to lidocaine.

3.5 Special Populations

Children: Children are excluded from this protocol as there is no direct benefit to the participants, the risk from the skin biopsies is small but above minimal, the procedure is invasive and can be stressful for children, and there is concern over their ability to maintain the LeFlap dressing.

Women: Pregnant and breastfeeding women are excluded from trial participation as there is no direct benefit to the participants.

Adults who lack capacity to consent: Adults lacking decision-making capacity to provide informed consent are excluded at screening as there is no direct benefit to the participants. Enrolled participants who permanently lose the ability to consent during participation will be monitored for safety but will have no additional research procedures performed.

NIH staff: NIH staff and family members of study team members may be enrolled in this study as this population meets the study entry criteria. Neither participation nor refusal to participate as a subject in the research will have an effect, either beneficial or adverse, on the participant's employment or position at NIH.

Every effort will be made to protect participant information, but such information may be available in medical records and may be available to authorized users outside of the study team in both an identifiable and unidentifiable manner.

The NIH Information Sheet on NIH Staff Research Participation will be made available. Please see Section 16 for consent of NIH Staff.

4 STUDY PROCEDURES

4.1 Initial Visit

After written informed consent is obtained, participants will have a history and a physical examination performed. Blood will be drawn and tested for Lyme serologies (approximately 8 mL of blood). Patients with acute EM will also have blood collected for culture, PCR, and other direct tests for *B. burgdorferi* (approximately 50 mL). These tests may be performed at NYMC, NIH, and Tufts laboratories. This initial visit may or may not be combined with the tick placement visit (see below).

4.2 Tick Placement Visit

This visit may occur together with the initial visit, or may be a separate visit, up to 1 month apart. If a separate visit, eligibility criteria will be reviewed again to ensure patient remains eligible. At this visit, approximately 40 mL of blood will be drawn and a urine sample may be collected and stored for future study related research. Stored specimens will be useful for future development of new diagnostic tests or to test for as yet to be identified emerging infectious agents. Female patients of childbearing potential will have a urine or blood pregnancy test performed at this visit. The results of the pregnancy test will be reviewed before the placement of the ticks. Self-reported symptoms will be characterized using symptom scales, the SF-36v2 questionnaire, and fatigue scales.

Except for patients with acute EM, ticks will not be placed at this visit if the individual is found to have abnormal vital signs (temperature $>38.0^{\circ}\text{C}$, a pulse greater than 105 beats per minute, systolic blood pressure $>160 \text{ mm/Hg}$ or diastolic blood pressure $>95 \text{ mm/Hg}$, in at least 2 measurements) and these individuals will be asked to follow up with their personal physician. They may be re-evaluated for tick placement at a subsequent time when the vital signs are within acceptable limits.

Skin Biopsy

[figure not shown]
Eligible participants (acute EM, untreated Lyme arthritis and PTLDS) who agree to undergo the optional skin biopsy will have two 2 or 3 mm skin punch biopsies performed outside the site of the tick placement. The skin will be cleansed and anesthetized with 2 percent lidocaine with epinephrine. Each biopsy will be performed using a “punch”- a small disposable tubular knife. The wound will be closed, if necessary, with steri-strips or (rarely) with 1 or 2 interrupted nylon sutures. A bandage will be applied and participants will receive the instruction sheet regarding follow up procedures ([Appendix 1](#)). If suture(s) are placed, patients will be asked to return in 7 to 10 days to have the suture(s) removed. Biopsies will not be done on face, neck, scalp, or over the tibia. One biopsy will be used for *B. burgdorferi* culture and/or PCR. A second biopsy will be stored for future study related research.

If the Initial Visit and the Placement Visit do not occur together, the initial skin biopsy may be performed at either visit, accordingly to the preference of the participant and study personnel.

Xenodiagnosis

Between 25-30 larval ticks that have been aged and are known to be ready to attach will be placed (Figure 1). The area chosen for the placement will be as close as possible to the site of the previous EM, if possible. Ticks will not be attached to head, neck or genitalia. If necessary, body hair will be shaved at the site. The ticks will be placed inside the Creature Comforts II LeFlap™ dressing which has been modified for tick use with the addition of a foam inner layer. The LeFlap is a pre-assembled confinement dressing that is used with medical maggots. Participants will be requested to keep the dressing dry for the duration of the attachment. Participants will receive an instruction sheet with instructions regarding care of the dressing and a Diary Card. The subject will be asked to complete a diary card daily starting the date of placement of the ticks through 30 days after tick removal.

Figure 1: Feeding of *Ixodes* Larvae under LeFlap Dressing

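### Research skin biopsies may be taken before the only pregnancy test described, although pregnancy excludes a woman from the whole trial

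*Combined protocol and SAP*

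**What the plan says.** Section 3.3 puts pregnancy in the general exclusion list. Section 3.4, the separate list for the biopsy component, does not mention it. Section 3.5 gives the scope and the reason: "Pregnant and breastfeeding women are excluded from trial participation as there is no direct benefit to the participants".

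Section 4.2 describes the test. "Female patients of childbearing potential will have a urine or blood pregnancy test performed at this visit", meaning the Tick Placement Visit, and "The results of the pregnancy test will be reviewed before the placement of the ticks". The biopsy is not mentioned in connection with the test.

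On timing, section 4.2 says of the placement visit: "This visit may occur together with the initial visit, or may be a separate visit, up to 1 month apart". Of the biopsy it says: "If the Initial Visit and the Placement Visit do not occur together, the initial skin biopsy may be performed at either visit", the choice being left to the participant and the staff.

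Sections 4.2 and 4.10 offer a biopsy before tick placement to three groups: acute erythema migrans, untreated Lyme arthritis and PTLDS. It consists of two punches of 2 or 3 mm under lidocaine with epinephrine. The post-therapy group and the healthy volunteers are biopsied only after tick removal.

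**The concern.** An exclusion from trial participation should be checked before the first research procedure that carries risk and offers no benefit. Here the check is attached to the ticks, while an earlier procedure is expressly allowed without it. A woman could consent, have two punch biopsies at the Initial Visit, and be found pregnant at the placement visit. The site would have followed the visit schedule exactly and still have carried out a research procedure on someone the protocol excludes.

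What is at stake is participant protection and an avoidable eligibility deviation. The reason given for excluding pregnant women, that they gain no direct benefit, applies to a research biopsy as much as to the ticks.

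**Working it through.** No formula applies. The check sets the eligibility rules beside the visit sequence.

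**1. Scope of the exclusion.** Sections 3.3 and 3.5 exclude pregnant women from the study as a whole, not from tick placement alone.

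**2. What is known at the Initial Visit.** Section 4.1 lists consent, history, physical examination, blood for Lyme serology and, in acute erythema migrans, blood for direct tests. It lists no pregnancy test.

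**3. What is known at the Tick Placement Visit.** Section 4.2 adds the pregnancy test, with review of the result before ticks are placed. It also requires a second eligibility review if the visits are separate. Both come after a biopsy taken at the Initial Visit. Section 4.7 likewise ties the exclusion check to the time of tick placement.

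**4. Permitted sequences.**

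| Schedule | Biopsy | Pregnancy test | Result required before biopsy? |
|---|---|---|---|
| Separate visits, biopsy at Initial Visit | Initial Visit | Placement visit, up to 1 month later | No |
| Separate visits, biopsy at placement visit | Placement visit | Same day | No order stated |
| Combined visit | Same day | Same day | No order stated |

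**5. Size by group** (group sizes from section 3.2).

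- Post-Lyme complaints at least 12 months from treatment, N=40, taken here to be the group that section 4.2 calls PTLDS: up to 1 month. Nothing in the text shortens it.
- Untreated Lyme arthritis, N=40: up to 1 month on paper. However, section 3.2 defends delaying therapy only for a few days and allows antibiotics once the ticks are collected, usually at 4-5 days and at most 7. A long wait before placement fits that poorly.
- Acute erythema migrans, N=40: about 2 days, because inclusion requires less than 48 hours of antibiotics. This assumes that the criterion must still hold at placement, as the second eligibility review implies.
- Post-therapy (N=100) and healthy volunteers (N=20): not affected, because their biopsies follow tick removal and so follow the test.

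The pre-placement biopsy is offered to at most 40 + 40 + 40 = 120 participants, and the 1-month gap is open on paper to at most 40 + 40 = 80 of them. These are ceilings. The number exposed is smaller: women of childbearing potential who accept the optional biopsy and have it before their test result is reviewed. The documents give no figure for any of these conditions, so no expected count can be derived.

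**The case against.** The strongest reply is that the protocol already limits the biopsy to eligible participants. A second eligibility review implies a first one, history and examination come before any procedure, and unwillingness to use birth control is itself an exclusion. A pregnancy known to the participant should therefore come out at the Initial Visit. This narrows the gap but does not close it: none of these steps is a test, and the protocol itself judged a test necessary before ticks are placed.

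A second reply is that the documents show no pregnancy-related hazard from the biopsy. That is correct. Section 3.4 leaves pregnancy out of the biopsy exclusions, and section 5.3 names no such risk. Section 3.5 does say that "the risk from the skin biopsies is small but above minimal", but in the paragraph that explains why children are excluded. It describes the procedure in general and is not a finding about pregnant women. A reader might infer that early biopsies endanger a pregnancy; the documents do not support that. What they do show is a breach of a stated exclusion.

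A third reply is that a 1-month gap will be rare. For acute erythema migrans it is effectively ruled out, and for untreated arthritis it is unlikely. A reader who applies the full month to all 120 participants would overstate the point.

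**Conclusion.** The inconsistency is real. The exclusion covers the whole trial, the only test described controls tick placement alone, and section 4.2 allows a biopsy before it. Missing detail does not explain this, because the early biopsy is expressly permitted. In practice the long gap matters mainly for the 40 participants with persistent symptoms. The unset order on the day of a combined visit can arise in all three groups offered a pre-placement biopsy.

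Severity is low. No endpoint, and no part of the powered comparison of symptomatic with asymptomatic patients, depends on it.

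A reader might extend the argument to healthy volunteers, whose serology can be drawn on the day ticks are placed, and infer that the specificity estimate is compromised. The documents do not support that. Negative serology is already an inclusion criterion in section 3.2, so placing ticks without it would breach the protocol. Only the result could arrive late, and turnaround time is not given. The criterion does not require the qualifying test to be the one drawn at the Initial Visit. Nothing in section 7.1 keeps an ineligible volunteer among the controls.

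The verdict rests on three assumptions: that PTLDS in sections 4.2 and 4.10 means the group with complaints at least 12 months from treatment, that the 48-hour criterion applies at placement, and that no pregnancy test beyond the one described is intended at the Initial Visit.

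**What to change.** Reconcile sections 4.1 and 4.2 with the exclusion in sections 3.3 and 3.5:

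- State that, for women of childbearing potential, a urine or blood pregnancy test is done and its result reviewed before the first research biopsy, at whichever visit that takes place.
- Keep the existing test and review before tick placement.
- State that on a day when both biopsy and tick placement occur, the result is reviewed before either.
- Carry the same order into section 4.7, which repeats the procedures, including the optional biopsy, after a positive xenodiagnosis.

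The cost is at most one extra pregnancy test for each woman who has a biopsy at a separate Initial Visit. At a combined visit there is no extra test, only a stated order. Sample size, analyses and the number of visits are unchanged.

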4.3 Tick Removal (4-6 days after tick placement)

Larval ticks typically feed for 4 to 5 days but it is possible that some might feed as long as 10 days. Participants will return to the study clinic for removal of the dressing and recovery of the ticks at 4-6 days. Pictures may be taken of the site. Approximately 40 mL of blood will be drawn for future study related research. Participants will be asked during the visit whether there were any complications during the feeding of the ticks, including adverse reactions and tick escape, and the diary card will be reviewed at this visit.

If there are a significant number of ticks still attached, the individual may be asked to return over the next subsequent days for evaluation until the majority of the ticks have detached. If this occurs, the ticks that dropped off will be collected, the dressing will be changed, and the individual will be seen within 24-72 hours for removal of the other ticks and completion of the visit. These visits may need to be repeated up to day 10 from the time of placement.

Eligible participants who agree to undergo the optional skin biopsy will have two 2 or 3 mm skin punch biopsies performed outside the site of the tick placement. The skin will be cleansed and anesthetized with 2 percent lidocaine with epinephrine. Each biopsy will be performed using a “punch”- a small disposable tubular knife. The wound will be closed, if necessary, with steri-strips or (rarely) with 1 or 2 interrupted nylon sutures. A bandage will be applied and participants will receive the instruction sheet regarding follow up procedures ([Appendix 1](#)). If suture(s) are placed, patients will be asked to return in 7 to 10 days to have the suture(s) removed. Biopsies will not be done on face, neck, scalp, or over the tibia. One biopsy will be used for *B. burgdorferi* culture and/or PCR. A second biopsy will be stored for future study related research.

The study team will contact each subject 7-10 days post-tick removal to determine if they are experiencing any AEs. The participants will also be instructed to call the study staff if any new symptoms occur during the period when the ticks are attached and for 30 days after tick removal. A 30-day window was chosen for the following reasons: 1) Adverse reactions to tape or the tick bites are expected to resolve within 2 weeks after removal of the ticks; 2) in the very unlikely event that there is an as yet unidentified infection that is transmitted by the ticks, all of the known

tick transmitted diseases have an onset of symptoms within 30 days of tick detachment. Participants will be specifically told to contact the study personnel for any fever, chills, joint pains, muscle pains, neck stiffness, or severe headache, as these are symptoms of known tick-borne diseases. For the first month after removal of the ticks, the participants will be asked to maintain a daily diary, which will be collected at the 1-month visit.

4.4 1-Month and 3-Month Follow-up

In addition to the contact with the individual at 7-10 days post-tick removal, participants will be followed at 4 to 6 weeks after the removal of ticks to ensure that no unanticipated events have occurred. This visit may be in person or by phone. Participants will be specifically questioned about fever, rash or infection at the site of tick attachment. They will be questioned about any intercurrent illnesses. Self-reported symptoms will be characterized using symptom scales, the SF-36v2 questionnaire and fatigue scales. Forms are self-administered and can be administered in paper form or computer, including online. If the visit is in person, approximately 40 mL of blood will be drawn and a urine sample may be collected for storage for future study related research. The diary card will be reviewed at this visit.

Participants will also be followed at 3 months (± 2 weeks) after the mesh is removed. This visit may be in person or by phone. Participants will be questioned about any intercurrent illnesses. They will complete the symptom scales, the SF-36v2 questionnaire and fatigue scales. Forms are self-administered and can be administered in paper form or computer, including online. If the visit is in person, approximately 40 mL of blood will be drawn and a urine sample may be collected for storage for future study related research.

Participants will be contacted to discuss their individual results from xenodiagnostic studies when these become finalized. The results are expected to be available within one year of the procedure.

4.5 12 Months after Start of Antibiotic Therapy

Participants enrolled under the Lyme disease, post treatment group will also be contacted at 12 months (± 4 weeks) after the start of their antibiotic therapy for Lyme disease. This visit may be in person or by phone. If the visit is in person, approximately 40 mL of blood will be drawn and a urine sample may be collected for storage for future study related research. Self-reported symptoms will be characterized using symptom scales, the SF-36v2 questionnaire and fatigue scales. Forms are self-administered and can be administered in paper form or computer, including online.

